9.3 Use of Controls

In this clinical study, there is no control group, no use of blinding techniques and no randomization distribution system.

9.4 Statistical Analyses

9.4.1 Overview

The data will be summarized in tables listing the mean, standard deviation, median, minimum, maximum and number of patients for continuous data, or in tables listing count (frequency) and percentage for categorical data.

All statistical analyses will be performed, and data appendices will be created, using the SAS[®] or Stata system. The effects of noncompliance, dropouts and possible covariates will be assessed to determine the impact on the general applicability of results from this study; however, no imputation for missing data will be performed. The results will be presented descriptively or in listings.

9.4.2 Patient disposition

Patient disposition will be tabulated; the number of enrolled, treated, prematurely terminated and completed patients will be summarized. Baseline demographics and characteristics will be summarized at the level of patient.

A list of dropouts will be prepared including reason for discontinuation and time of discontinuation.

9.4.3 Primary safety analysis

The primary safety analysis will be performed on the safety analysis set. Frequency distribution of patients with ShortCut device and/or ShortCut procedure related mortality and/or stroke events, as determined by the CEC, and assessed at discharge or at 7 days post-procedure, whichever occurs first, will be presented, along with the 95% confidence intervals.

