5.1 Primary endpoints

5.1.1 Primary safety endpoint

Each of the following ShortCut[™] device and/or ShortCut[™] procedure-related serious adverse events will be assessed at discharge or at 7 days post-procedure, whichever occurs first:

- Mortality
- Stroke (fatal, disabling and non-disabling)

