5.1.2 Primary effectiveness endpoint

Overall leaflet splitting success using the ShortCut[™] device assessed intra-procedurally by echocardiography and or angiography.

Per patient leaflet splitting success will be determined as follows:

- For patients in whom one leaflet was intervened, splitting success per patient will be determined based on the splitting success of the intervened leaflet:
 - Visualization of leaflet split, assessed by intraprocedural TEE immediately post-ShortCut[™] procedure and prior to TAVR, OR
 - Increase in aortic regurgitation from pre to post leaflet split, assessed by intraprocedural TEE or angiography.
- For patients in whom two leaflets were intervened, splitting success per patient will be determined based on the splitting success of the first intervened leaflet.

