- 25. Known hypersensitivity or contraindication to all intra-procedural anticoagulation or any product material (Nitinol alloys, stainless steel, Polyamide 12, Polyether block amide, Polytetrafluoroethylene (PTFE, Teflon), Polyphenylsulfone (PPSU), Polyvinyl chloride (PVC, DEHP Free), Polypropylene (PP), SurModics Serene coating (PhotoLink[®] surface modification), Silicone, Epoxy adhesive, Acrylic glue).
- 26. Pregnant women or women planning a pregnancy within 1 month of study enrollment.
- 27. Need for emergency surgery for any reason.
- 28. Inoperable for emergency open-heart surgery.
- 29. Patient has a condition that, in the opinion of the Investigator or the Screening Committee, precludes the patient from undergoing the index procedure.
- 30. Life expectancy is less than one year.
- 31. Patient is currently participating in another investigational drug or device study. Note: Studies requiring extended follow-up for products that were investigational, but have since become commercially available, are not considered investigational studies. Observational studies are not considered exclusionary.
- 32. Patient is unwilling to participate or unwilling to return for study follow-up activities.
- 33. Patient is unable to consent to participate, unless the subject has a legally authorized representative.

8 Study schedule and time points

	Screening	Baseline	Index procedure	Pre- discharge	30 days post- procedure	90 days post- procedure
Informed consent	Х					
Medical and surgical history review	Х	Х				
NYHA classification	Х				Х	
Risk assessment, including	Х					
EuroSCORE II and STS score						
Physical examination		Х			Х	
Blood tests ¹		Х		Х		
12-lead ECG	Х	Х		Х	Х	
Modified Rankin Score and NIHSS ⁸		Х		X ⁷	X ⁷	
5 Meters-Walk Test		Х				
Katz Activities of Daily Living (ADL)		Х				
CT of heart, aortic root, and aortic	X ²					
arch						
Echocardiographic imaging	X ³	X ⁵	X ⁶	Х		
Invasive or CT coronary angiography	X ⁴					
ShortCut [™] assisted TAVR			Х			
Angiography for coronary patency			Х			
Adverse events recording		Х	Х	Х	Х	Х
Medications recording		Х	Х	Х	Х	Х
Clinical status remote evaluation						Х

¹ The relevant blood assays are listed above in each timepoint section.

² CT scan will be performed only in case no adequate CT scan was performed within 6 months prior to screening.

³ TTE at screening will be performed only in case no adequate TTE was performed within 90 days prior to screening.

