TAVR clinical studies, a sample size of a minimum of 60 patients for whom the ShortCut[™] procedure was initiated will allow capturing relatively rare Adverse Events (AEs), such as stroke and all-cause mortality, with high probability. The expected rates of stroke and all-cause mortality in ViV TAVR studies are estimated at 1.4% and 3.5%, respectively. The rates of stroke and all-cause mortality reported for ViV TAVR small studies (N ≤ 70) tend to be somewhat larger, and with much wider confidence intervals. Due to this difference in rate variability, a minimum of 60 patients for whom the ShortCut[™] procedure was initiated will allow demonstrating that the stroke rate (lowest of the two) does not increase more than 2-fold (i.e., more than 2.8%) compared to reported rates in ViV TAVR studies.

A sample size of a minimum of 60 patients with an initiated ShortCut[™] procedure will allow detecting at least 1 event whose incidence in the intended use patient population is 2.8% with high probability (>80%), and thus to estimate the incidence of stroke and all-cause mortality in the intended use patient population.

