9.4.4 Secondary safety analysis

The secondary safety analysis will be performed on the safety analysis set. Frequency distribution of all AEs listed in section **Error! Reference source not found.** will be presented by body system and preferred term, severity and relation to ShortCut device and/or ShortCut procedure, as determined by the CEC. For each AE of interest, the tabulation will include the number of AEs and the number and percentage of patients experiencing it.

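### Primary safety counts only ShortCut-attributed death and stroke, while the Section 9.2 reference rates are unfiltered; the all-cause rates that would match them have no stated confidence interval

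*Combined protocol and SAP*

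**What the plan says.** **Endpoint.** Section 5.1.1 defines primary safety as "Each of the following ShortCut[™] device and/or ShortCut[™] procedure-related serious adverse events", namely death and stroke, up to the earlier of discharge and day 7. Section 9.4.3 analyses it on the safety set as "Frequency distribution of patients with ShortCut device and/or ShortCut procedure related mortality and/or stroke events, as determined by the CEC", with 95% confidence intervals. It sets no limit and no pass rule.

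**Setting.** Section 5.1.2 has the split imaged after the ShortCut "procedure and prior to TAVR", and the schedule in Section 8 lists ShortCut "assisted TAVR" once, at the index procedure. Section 9.3 states that there is no control group and no blinding.

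**Reference rates.** Section 9.2 says that primary safety is not powered, then justifies a minimum of 60 initiated procedures by external data: "The expected rates of stroke and all-cause mortality in ViV TAVR studies are estimated at 1.4% and 3.5%, respectively". It adds that this number will allow a demonstration that the stroke rate does not more than double (2.8%), and that at least one event of 2.8% incidence would be seen with more than 80% probability. It does not say which stroke endpoint is meant, or over what period the reference rates were measured.

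**All-cause data.** Section 5.2.1 lists all-cause death and all-cause stroke through 30 days. Section 9.4.4 describes their reporting: "For each AE of interest, the tabulation will include the number of AEs and the number and percentage of patients experiencing it". (Its cross-reference does not resolve; I read it as pointing to Section 5.2.1.) Section 9.4.6 adds Kaplan-Meier estimates at days 30 and 90. None of these sections states an interval.

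**The concern.** The trial's only yardstick for safety is external, and it counts every stroke and every death in ViV TAVR studies. The death and stroke rate that the plan puts first, and the only one given an interval, counts the subset that the CEC attributes to ShortCut. A stroke assigned to the TAVR step leaves that numerator, while strokes of the same kind remain in the reference rate.

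The text of Section 9.2 makes the two easy to join. The 2.8% argument directly follows the statement that the primary safety endpoint is not powered, and speaks only of the stroke rate. A reader of the final report could set the related-only rate against 1.4% or 2.8% and find the device no worse than TAVR alone. The result would depend partly on an attribution judgement that an uncontrolled, unblinded design gives no means of checking.

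**Working it through.** **Inputs.** N = 60 (Section 9.2, minimum initiated procedures). Reference stroke rate 1.4%, and limit 2 × 1.4% = 2.8% (Section 9.2). The share *f* of strokes attributed to ShortCut is not in the documents, so I take 25%, 50%, 75% and 100% as assumptions.

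**1. The plan's own figure.** P(at least 1 event) = 1 − (1 − p)^60. With p = 0.028: 1 − 0.972^60 = 0.818. This agrees with the stated figure of more than 80%, provided that 2.8% is the rate of the events actually counted.

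**2. The same figure for the related-only count.** Related strokes are a subset of all strokes, so the counted rate is 0.028 × f, which cannot exceed 0.028.

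| Share attributed (assumed) | Counted rate | Expected events in 60 | P(at least 1) | P(none) |
|---|---|---|---|---|
| 100% | 2.8% | 1.68 | 81.8% | 18.2% |
| 75% | 2.1% | 1.26 | 72.0% | 28.0% |
| 50% | 1.4% | 0.84 | 57.1% | 42.9% |
| 25% | 0.7% | 0.42 | 34.4% | 65.6% |

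At a 50% share, a true doubling of stroke gives a counted rate equal to the 1.4% benchmark.

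**3. A larger true excess.** Suppose the true all-stroke rate is 5.6% (4 × 1.4%). An observed rate below 2.8% means 0 or 1 of 60, since 1/60 = 1.67% and 2/60 = 3.33%. The binomial probability of 0 or 1 event at rate 0.056 × f is 14.4% when all strokes are counted, and 27.7%, 49.6% and 79.5% for shares of 75%, 50% and 25%.

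**4. What N = 60 can show even with the right numerator.** With 0/60, the two-sided 95% Clopper-Pearson upper limit is 1 − 0.025^(1/60) = 6.0%; the one-sided 95% limit is 1 − 0.05^(1/60) = 4.9%. With 1/60, the two-sided upper limit is 8.9%. To bring the limit down to 2.8% with no events would take ln(0.025)/ln(0.972) = 129.9, so 130 patients (two-sided), or ln(0.05)/ln(0.972) = 105.5, so 106 (one-sided). A rate of at most 2.8% therefore cannot be demonstrated with 60 patients, whichever strokes are counted.

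**5. Which rates have an interval.**

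| Death/stroke rate | Window | Stated 95% interval |
|---|---|---|
| Related only (9.4.3) | earlier of discharge and day 7 | yes |
| All-cause | earlier of discharge and day 7 | not planned at all |
| All-cause (9.4.4) | 30 days | no |
| All-cause death and first stroke, Kaplan-Meier (9.4.6) | days 30 and 90 | no |

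**The case against.** The strongest reply is that the unlike comparison is not planned. Section 9.4.3 is descriptive, and Section 9.2 disclaims power for primary safety. Its wording about the incidence of stroke and all-cause mortality fits the all-cause endpoints of Section 5.2.1 better than the related-only one. All-cause events are tabulated to 30 days by relation to ShortCut, so a stroke assigned to TAVR stays visible in the report. A device-related primary endpoint with all-cause secondary endpoints is a legitimate design choice. All of this stands. A reader might infer that the plan contains a biased safety test, or that it would conceal a doubling of stroke; the documents support neither.

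Other limits also stand:

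- The attributed shares are assumed. A reader might infer that strokes around the procedure will mostly be assigned to TAVR, or cannot be assigned to either step. The document, a synopsis, gives no attribution rules, so that cannot be judged. The subset argument does not need it.
- A reader might take Section 9.4.3 to hold the only interval on a safety outcome. It does not: Section 9.4.8 gives intervals for leaflet-related coronary obstruction and intervention within 30 days, and Section 9.4.11 for technical success. The gap concerns all-cause death and stroke.
- The direction is certain only for each component. Section 9.4.3 can be read as a combined death and/or stroke count, whereas Section 5.1.1 assesses each event. A combined count set against the stroke-only 1.4% would push the other way.
- With 60 patients, only zero events gives an observed rate at or below 1.4%, and at a true 2.8% that has an 18.2% chance even when all strokes are counted. Small numbers alone can produce a reassuring figure.

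The reply does not supply an interval for any all-cause death or stroke rate, an all-cause rate in the primary window, or a statement of which stroke rate Section 9.2 means.

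**Conclusion.** The point holds as a gap in specification and reporting. The primary safety rate and the Section 9.2 reference rates count different events, Section 9.2 does not say which stroke rate its argument concerns, and the all-cause rates that would match lack intervals. If the related-only stroke or death rate were set against its own reference rate, the comparison would favour the device; by how much depends on the attributed share, which is unknown. At a true stroke rate of 2.8%, the chance of at least one counted stroke in 60 is 81.8% only with full attribution, and 72.0%, 57.1% or 34.4% at assumed shares of 75%, 50% or 25%.

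The length of follow-up may add to the mismatch, but the reference window is not stated, so this cannot be sized. Correcting the numerator would not rescue the two-fold claim: 0/60 still leaves an upper limit of 6.0%. The change is worth making because it is cheap and gives a safety estimate that does not depend on attribution. The primary endpoint can stay as it is.

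**What to change.** - **Section 9.4.3:** beside the related rates, show all-cause death and all-cause stroke, each separately, in the same discharge/day-7 window on the safety set, with exact 95% confidence intervals.
- **Section 9.4.4:** add exact 95% confidence intervals for 30-day all-cause stroke and 30-day all-cause death.
- **Section 9.2:** state the time window of the reference studies. State that any comparison with 1.4%, 2.8% or 3.5% uses the all-cause rates over that window and is descriptive only. Drop the claim that 60 patients can demonstrate that stroke does not exceed 2.8%.

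The cost is SAP wording and a few table rows. Adverse events are already recorded from baseline to day 90 (Section 8), so no new data are needed. The downside for the sponsor is that each all-cause figure will be equal to or less favourable than its related-only counterpart.

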9.4.4 Secondary safety analysis

The secondary safety analysis will be performed on the safety analysis set. Frequency distribution of all AEs listed in section **Error! Reference source not found.** will be presented by body system and preferred term, severity and relation to ShortCut device and/or ShortCut procedure, as determined by the CEC. For each AE of interest, the tabulation will include the number of AEs and the number and percentage of patients experiencing it.

9.4.5 Tertiary safety analysis

The tertiary safety analysis will be performed on the safety analysis set. Frequency distribution of all AEs listed in section 5.3 will be presented by body system and preferred term, severity and relation to ShortCut device and/or ShortCut procedure, as determined by the CEC. For each AE of interest, the tabulation will include the number of AEs, the number and percentage of patients experiencing it.

9.4.6 Additional safety analyses

Survival analysis of time to all-cause mortality and time to first stroke will be done using Kaplan-Meier curve. Estimates of all-cause mortality and stroke rates at day 30 and day 90 will be estimated based on the Kaplan-Meier curve.

All AEs and SAEs obtained throughout the 90 days of follow up will be coded and presented by body system, preferred term, severity and relation to the device and/ or procedure. AEs will be presented separately for the first month post-procedure, and the subsequent two months.

9.4.7 Primary effectiveness analysis

The primary effectiveness analysis will be performed on the primary effectiveness analysis set.

The primary effectiveness hypothesis will test whether the rate of patients with a successful split, exceeds the Performance Goal, set to 75%. The following primary effectiveness hypothesis will be tested:

 $H_0: P(split) \le 0.75$ $H_1: P(split) > 0.75$

where *P(split)* is the rate of Evaluable Patients with a successful split. Frequency distribution of Evaluable Patients with a successful split will be presented along with the Clopper-Pearson 95% confidence interval. The primary effectiveness null hypothesis will be rejected (i.e., the primary effectiveness hypothesis is met) if the lower limit of the confidence interval is above 0.75.

9.4.8 Secondary effectiveness analysis

The secondary effectiveness analysis will be performed on the secondary effectiveness analysis set.

Per Intervened Leaflet Splitting Success

The secondary effectiveness analysis will present the rate of successful splits along with the Clopper-Pearson 95% confidence interval.

The overall rate of successful splits will also be estimated via generalized estimating equations (GEE, SAS PROC GENMOD) that account for potential dependency between the two leaflets outcomes of the same patient.

Coronary Artery Ostia Obstruction and Intervention

The secondary effectiveness analysis will present the following:

- Frequency distribution and the corresponding 95% confidence interval of patients with:
 - Coronary artery ostia obstruction related to the intervened leaflet within 30 days post-procedure, as determined by the CEC
 - Coronary artery intervention related to the intervened leaflet within 30 days post-procedure, as determined by the CEC

For patients who experienced any of the above events, a by-patient listing will be provided with extended event description, time from the procedure and relation to ShortCut device and/or ShortCut procedure.

9.4.9 Per Protocol primary effectiveness analysis

For the Per Protocol primary effectiveness analysis, the primary effectiveness analysis will be repeated using the PPPE analysis set.

9.4.10 Per Protocol secondary effectiveness analysis

For the Per Protocol secondary effectiveness analysis, the secondary effectiveness analysis will be repeated using the PPSE analysis set.

9.4.11 Technical success analysis

The technical success analysis will be performed on the safety analysis set. Frequency distribution of patients with technical success will be presented along with a 95% confidence interval, including the rate of each individual component. For patients that did not have technical success, a by-patient listing will be provided with detailed description of the reason.

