5.2.3 Technical success endpoint

A composite of the following, which will be assessed at exit from procedure room following the ShortCut[™] procedure:

- Successful access, delivery, and retrieval of the ShortCut[™] device
- Freedom from ShortCut[™] device- and/or ShortCut[™] procedure-related mortality
- Freedom from ShortCut[™] device- and/or ShortCut[™] procedure-related:
 - Surgery or intervention
 - Major vascular or access-related complications
 - Cardiac structural complication

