7.2 Exclusion criteria

- An excessive aortic valve leaflet Calcium morphology, such as diffuse massive calcification at the targeted leaflet for splitting or anatomy not suitable for the use of the ShortCut[™] device, as determined by the CT core lab.
- 2. Leaflet planned to be intervened is torn pre-ShortCut device access.
- 3. Patient has iliofemoral vessel characteristics that preclude safe insertion of the introducer sheath.
- 4. Anatomy that does not allow safe placement of a cerebral embolic protection device.
- 5. Planned concurrent intervention in the same setting of the index procedure.
- 6. Surgery or interventional procedure ≤ 1 month prior to the index procedure.
- 7. Planned provisional (pre-position coronary artery) stents.
- 8. Coronary disease that, in the opinion of the local Heart Team, should be treated; or treatment of coronary disease ≤ 1 month prior to index procedure.
- Carotid or vertebral artery disease that, in the opinion of the local Heart Team, should be treated; or treatment of carotid stenosis ≤ 1 month prior to index procedure.
- 10. CVA or TIA \leq 6 months prior to index procedure.
- 11. Severe neurological disability, as determined by the Investigator.
- 12. History of a myocardial infarction (MI) ≤ 6 weeks prior to index procedure.
- 13. Current or suspected endocarditis on the aortic valve.
- 14. Identified thrombotic material on the valve by either CT or Echocardiography.
- 15. Cardiac imaging evidence of left ventricular intracardiac mass or thrombus.
- 16. Hemodynamic or respiratory instability requiring inotropic support, mechanical ventilation or mechanical heart assistance.
- 17. LVEF < 30%.
- 18. Ongoing severe infection or sepsis.
- **19**. Known current COVID-19 infection (with or without symptoms), recent positive test for COVID-19, or recent exposure to a person with COVID-19 infection.

- 20. Patient refuses blood transfusion.
- 21. Patient has renal insufficiency (GFR < 30 ml/min or serum creatinine > 2.5 mg/dL), or on chronic dialysis.
- 22. Patient with clinically significant abnormality in cell blood count as defined by WBC < 3000 cell/ μ L, Hb < 9 g/dL and platelet count < 90,000 cell/ μ L or history of bleeding diathesis or coagulopathy, or hypercoagulable states.
- 23. Active peptic ulcer with bleeding.
- 24. Known allergy to contrast media that cannot be adequately controlled with premedication.

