9.1 Study Analysis Sets

9.1.1 Safety analysis set

The safety analysis set will include all patients who reached the point of index procedure, i.e., patients in whom the ShortCut[™] device was introduced through the introducer sheath. Patients who were treated with the ShortCut[™] without meeting the eligibility criteria will also be included in this analysis set.

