9.1.3 Secondary effectiveness analysis set

The secondary effectiveness analysis set will include patients in whom the following ShortCut[™] procedure steps have been performed: access, delivery to the aortic valve, activation of the ShortCut[™] Splitting Element and split attempt.

All intervened leaflets of these patients will be included in the secondary effectiveness analysis set.

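### Technical success scores access of the device but is analysed only in patients whose device was already introduced through the sheath, so a failed introduction cannot count as a failure

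*Combined protocol and SAP*

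**What the plan says.** Section 5.2.3 defines technical success as a composite, "which will be assessed at exit from procedure room". Its first component is "Successful access, delivery, and retrieval", and the sentence goes on to name the ShortCut device as the object of all three.

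Section 9.4.11 fixes the analysis: "The technical success analysis will be performed on the safety analysis set". The result is a frequency with a 95% confidence interval, "including the rate of each individual component". It adds: "For patients that did not have technical success, a by-patient listing will be provided". No hypothesis, goal or interval method is given.

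Section 9.1.1 sets the entry condition of the safety set: the "device was introduced through the introducer sheath".

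The word access appears in two other relevant places. Section 9.1.3 refers to patients in whom the "procedure steps have been performed: access, delivery to the aortic valve" and later steps took place. Exclusion criterion 2 in section 7.2 reads: "Leaflet planned to be intervened is torn pre-ShortCut device access". Neither says where access begins.

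**The concern.** An analysis set should not be conditioned on the outcome it is used to measure. Here the set begins once the device has been introduced through the sheath, while the endpoint scores whether access of the device succeeded. Part of the first component is therefore met by construction, and the patients who would fail that part are never in the denominator.

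What is at stake is the published technical success rate, the rate for its access, delivery and retrieval component, and the completeness of the listing of technical failures. Omitted failures can only make these look better.

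**Working it through.** **Step 1. Follow one patient through the sections.** Introduction of the device is attempted, but it cannot be passed through the sheath.

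- Section 5.2.3: access of the device was not successful, so the composite is not met.
- Section 9.1.1: the device was not introduced through the sheath, so the patient is not in the safety set.
- Section 9.4.11: the rate, the component rates and the failure listing all use the safety set, so the patient appears in none of them.
- Section 9.2: the patient most naturally falls among the up to 10 enrolled patients lost before the procedure was initiated, under the residual category of reasons.
- Sections 9.4.1 and 9.4.2: dropouts are listed with reason and time, and their effect on applicability is assessed descriptively. Neither section counts the patient as a technical failure.

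**Step 2. Compare the two meanings of access.**

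| Meaning of access | Failures outside the set | Failures still counted |
|---|---|---|
| Device access only | Device could not be passed through the sheath | Any failure after introduction |
| Also vascular or sheath access | The above, plus failed vascular or sheath access | Any failure after introduction |

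The first row is lost under both meanings. The second row adds to it only under the wider one.

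**Step 3. Direction and size.** The documents give no expected technical success rate and no failed-introduction rate, so there is no planned figure to reproduce. Let n be the size of the safety set, s the successes in it, and k the omitted failures.

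- Planned rate: s/n.
- Rate with the omitted failures counted: s/(n + k).
- Difference: s/n − s/(n + k) = (s/n) × k/(n + k). This is never negative, so any bias is favourable.

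Inputs: n = 60 is the minimum in section 9.2, and n = 70 adds the up to 10 further patients with an initiated procedure. The values of s and k are assumed. Lower limits are Clopper-Pearson, also assumed here because section 9.4.11 names no method. For s = n the limit is 0.025^(1/n), for example 0.025^(1/60) = 0.9404. Otherwise it is the 2.5% quantile of Beta(s, n + k − s + 1).

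| n | s | k | Rate counting k | 95% lower limit |
|---|---|---|---|---|
| 60 | 60 | 0 | 60/60 = 100% | 94.0% |
| 60 | 60 | 1 | 60/61 = 98.4% | 91.2% |
| 60 | 60 | 2 | 60/62 = 96.8% | 88.8% |
| 60 | 60 | 3 | 60/63 = 95.2% | 86.7% |
| 70 | 70 | 0 | 70/70 = 100% | 94.9% |
| 70 | 70 | 1 | 70/71 = 98.6% | 92.4% |
| 60 | 57 | 0 | 57/60 = 95.0% | 86.1% |
| 60 | 57 | 1 | 57/61 = 93.4% | 84.1% |

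In these examples one omitted failure moves the estimate by 1.4 to 1.6 percentage points and the lower limit by 2.0 to 2.8.

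**Step 4. Why the reason for stopping matters.** Suppose 63 patients come to an attempted introduction, three are not introduced, only one of those stops is access-related or device-related, and the other 60 succeed. The plan reports 60/60 = 100%. Counting the one relevant failure gives 60/61 = 98.4%. Scoring all three as failures gives 60/63 = 95.2%, which overcorrects.

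**The case against.** The strongest reply is that the set fits the endpoint. Section 5.2.3 speaks of access of the device, and exclusion criterion 2 speaks of device access. Sections 9.1.1 and 9.2, read together, place the start of the procedure at introduction of the device. The endpoint is assessed at the end of that procedure, so a patient in whom it never began may seem to have nothing to assess.

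Much of this stands. The wording leans towards device access. A reader might infer that the plan drops every failed vascular puncture or sheath placement from an endpoint meant to score it. The documents do not support that, because they do not say that access reaches back so far. This text is also a synopsis: Figure 1 is not shown, and the section 8.2.1.2 cited in section 9.2 is not included. Either may settle the terms.

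The reply does not remove the narrower gap. If access means device access, a device that could not be passed through the sheath is a plain example of its failure, and that patient is still outside the set.

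Three further points limit the size:

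- Exclusion criterion 3 removes patients whose iliofemoral vessels preclude safe sheath insertion, so such failures should be few.
- Non-introduced patients are not hidden. The dropout list gives their reasons, and a reader could recompute the rate from it.
- A reader might take the 10 places for pre-procedure dropouts in section 9.2 as a measure of omitted failures. They are a planning ceiling that covers death, withdrawal, loss to follow-up and other reasons, and say nothing about how many would be failed introductions.

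**Conclusion.** The point holds in a limited form. Under either meaning of access, an attempted but failed introduction cannot count against technical success. Under the wider meaning, failed vascular or sheath access is left out as well, but that remains conditional.

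The bias, if any, is favourable. Its size is unknown and probably small: about 1.6 percentage points per omitted failure when all 60 patients in the set succeed, and zero if there are none. This rests on assumed counts, on exact limits, and on reading section 9.1.1 as requiring that the device passed through the sheath.

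It should not be read as an error in the safety set, nor as a threat to the primary results. The primary effectiveness analysis uses a different set, the primary safety analysis does not use this endpoint, and technical success is descriptive. This is a cheap improvement that the sponsor could make.

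**What to change.** Leave section 9.1.1 and the primary analyses as they are. In section 9.4.11:

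- Analyse technical success in the safety set plus enrolled patients in whom introduction of the ShortCut device was attempted but failed for access-related or device-related reasons. Count these patients as technical failures, and include them in the component rates and the failure listing.
- Extend this to failed vascular or sheath access only if the protocol's meaning of access includes it. Otherwise report those failures alongside the rate.
- List patients stopped for unrelated reasons, such as withdrawal or a leaflet found torn, separately with the reason, and do not score them as failures.
- Repeat the analysis on the safety set as supporting.

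The cost is SAP wording, a classification of the few non-introductions by reason, and possibly one case report form field for attempted introduction and the reason it failed. No follow-up is added, since the endpoint closes at exit from the procedure room. Classifying the reason takes some judgement in an open-label study. The SAP gives the CEC event relatedness and coronary events, not this task, so the plan should say who does it. The reported rate may also be slightly lower.
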